5.1 Study Periods and Visit Window Definitions

5.1.1 Study Periods

The study consists of 3 periods: screening, treatment (with no maximum number of cycles defined), and a follow-up period (end of treatment, long-term follow-up). Results will be presented by time point and not by period. However, the naming of the time points will reflect the period. In the investigational treatment arm, a patient will be treated with ¹⁷⁷Lu-PSMA-617 + BSC/BSoC up to a maximum of 6 cycles, and then BSC/BSoC only for the duration of the on-treatment period. Note that for cycles 1-6, cycle duration is 6 weeks, and for cycles 7 and beyond, cycle duration is 12 weeks.

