5.1.2 Visit Windows

For data collected at multiple time points, the scheduled collection date/time will be used to summarize the data, unless otherwise indicated. Visits are scheduled from time of previous cycle's Day 1.

Scan assessments are scheduled from the reference date (date of first dose). Scan dates are not associated with a visit number. Dates are used for analyses and patient listings.

Unscheduled assessments will not be taken into account in summary variable calculations, except for baseline assessments and unscheduled RECIST, bone scan, PSA and HRQoL evaluations for evaluating efficacy (Section 8). All measurements will be presented in the listings.

Unless otherwise indicated, if more than one measurement (a lab result for example) exists for a patient on a particular time point/visit, the last value obtained at that time point/visit will be used when summarizing the data.

Refer to protocol section 6.1 and protocol Appendix 1 for schedules of study assessments during each study period.

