8.2.3.3 Quality of Life (QoL) Analysis

For QoL analyses, patient reported outcomes (PROs) will be assessed using the questionnaires EQ-5D-5L, FACT-P, and BPI-SF.

Analyses will be done on the PFS-FAS, and all results will be reported by treatment arm. QoL measures are collected on Day 1 of each treatment cycle and at the EOT visit. Analyses over time will include time up through EOT visit.

For analysis of each outcome, only patients with a baseline value and at least one post baseline time point will be included. As with all efficacy analyses, main models will be adjusted for randomization stratification factors. Type I error is not controlled in the multiple health related QoL analyses. Thus, all p-values presented will be unadjusted and are nominal and descriptive.

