Since utility score depends on the combination of all items' responses, any missing response results in a missing utility score. If a patient dies, for analysis he will be assigned a score of 0 on the date of death. In the U.K. value set, utility scores ranges from the lowest possible score for a living patient of -0.594 (when all responses are '5') to 1 (when all responses are '1').

Analysis

For each of the five dimension-scales, frequency count and percentage of each reporting level (1 to 5) over time will be presented.

Utility score and EQ-VAS, will be summarized as continuous variables and will be presented for each time point. For EQ-VAS and Utility score, a plot of the mean values with standard errors by treatment group at each time point (showing number of subjects at each visit), will be constructed.

The proportion of patients and associated 95% CI who experience any improvement relative to baseline in utility score (an increase of .001 or more) at any time up through EOT will be summarized for each treatment.

Similarly, the proportion of patients with worsening relative to baseline, indicated by no change or any decrease in score, will be summarized.

Time to worsening for utility score is defined as the time (in months) from randomization to the first occurrence of worsening in score relative to baseline (no change or any decrease), clinical disease progression (excluding radiographic and PSA progression), or death, whichever is earlier. If no event is experienced, the censoring date will be time of the last QoL assessment.

Survival curves for the time to worsening (months) for each treatment arm will be computed using the Kaplan-Meier method. The two treatment arms will be compared using a cox regression analysis stratified for randomization stratification factors (LDH \leq 260 UI/L vs \geq , liver metastases (yes vs no), ECOG (0-1 vs 2), Inclusion of NAAD in BSC/BSoc at time of randomization (yes vs no)). The 25th percentile of and median time to worsening will be presented, in case less than 50% of subjects experienced worsening for some variables.

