$$\frac{\text{PWB score}}{\text{PWB score}} + \frac{\text{SFWB score}}{\text{SFWB score}} + \frac{\text{EWB score}}{\text{EWB score}} + \frac{\text{FWB score}}{\text{FWB score}} = \text{FACT-G Total score}$$

To derive a FACT-P Total score:

Score range: 0-156

$$\frac{\text{PWB score}}{\text{PWB score}} + \frac{\text{SFWB score}}{\text{SFWB score}} + \frac{\text{EWB score}}{\text{EWB score}} + \frac{\text{FWB score}}{\text{FWB score}} + \frac{\text{PCS score}}{\text{PCS score}} = \text{FACT-P Total score}$$

To derive Pain-related subscale (PRS):

Subscale	Item Code	Reverse item?	Item response	Item Score
Pain-related subscale	P1	4	-	=
	P2	4	-	=
	P3	4	-	=
Score range: 0-16	GP4	4	-	=
Sum individual item scores:				
Multiply by 4:				
Divide by number of items answered:				= PR Subscale score

To derive FACT Advanced Prostate Symptom Index-8 (FAPSI-8):

Using the 8 items GP1, GP4, GE6, C2, P2, P3, P7, P8, do the following:

Reverse code individual items as needed following guidelines in scores above.

Sum individual item scores.

Multiply by 8.

Divide by the number of items answered.

Analysis

For each FACT-P related total scale and subscale described in the table in the Description section above, will be summarized as continuous variables and will be presented for each time point. A plot of the mean values with standard errors by treatment group at each time point (showing number of subjects at each visit), will be constructed for FACT-P total scale only.

Subscale analysis criteria:

When a treatment difference in the time to worsening in FACT-P total score results in a $p < 0.05$, the FACT-P total subscales defined above (PWB, SFWB, EWB, FWB, PCS) will be analyzed to determine which are associated with the differences.

The proportion of patients that experience improvement relative to baseline in FACT-P total score indicated by a ≥ 10 point increase at any time up through EOT will be summarized as described in Section 8.2.3.3.1 for EQ-5D-5L utility score, and subsequently for the subscales when the .05 criteria described above is met.

The proportion of patients that experience worsening relative to baseline in FACT-P total score indicated by a ≥ 10 point decrease will be summarized similarly.

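### Quality-of-life improvement counted at any visit through end of treatment gives the longer-treated arm more chances, adding about 3 to 6 points of improvers with no true change

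*SAP*

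**What the plan says.** SAP 8.2.3.3.1 gives, for each arm with a 95% CI, the proportion of patients "who experience any improvement relative to baseline in utility score (an increase of .001 or more) at any time up through EOT". SAP 8.2.3.3.2 does the same for FACT-P total, with a "10 point increase at any time up through EOT". It extends the FACT-P total analyses to PRS, FAPSI-8, TOI and FACT-G with their own thresholds, and to the five FACT-P subscales if the time-to-worsening result has p below 0.05. Both sections also give a matching proportion worsened.

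On timing, SAP 8.2.3.3 says "QoL measures are collected on Day 1 of each treatment cycle and at the EOT visit" and "Analyses over time will include time up through EOT visit". SAP 5.1.1 states that for cycles 1 to 6 "cycle duration is 6 weeks, and for cycles 7 and beyond, cycle duration is 12 weeks". SAP 5.1.2 also admits "unscheduled RECIST, bone scan, PSA and HRQoL evaluations for evaluating efficacy". The denominator is patients with a baseline and at least one later value.

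On death, SAP 8.2.3.3.1 states that "for analysis he will be assigned a score of 0 on the date of death", while living states reach down to -0.594.

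Neither section sets a fixed window, asks for confirmation, or adjusts for the number of questionnaires. Elsewhere the SAP does require confirmation, of RECIST response (8.1.2) and PSA response (8.1.3), each at least 4 weeks later.

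**The concern.** A count of patients who ever qualify rises with the number of looks. Here the number of looks is set by time on treatment. Protocol 3.4.5 lets treatment run until radiographic progression, among other reasons, and the plan expects progression to come later in the investigational arm. That arm will therefore complete more questionnaires and, as long as scores vary from visit to visit, show more improvers even if the treatment does nothing for quality of life. A threshold of 0.001 lets almost any rise in utility count.

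At stake is the reading of a simple figure, percent improved by arm with confidence intervals. A reader would naturally compare the two arms, and part of the difference would reflect how long patients were observed.

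**Working it through.** **Inputs from the documents.** Median rPFS 4 months (control) and 6 months (active), 364 events, one-sided alpha 0.004, about 557 patients in the PFS-FAS (SAP 3.4); 2:1 allocation (SAP 3.1); questionnaires on Day 1 of each cycle and at EOT (SAP 8.2.3.3); cycles of 6 weeks, then 12 weeks from cycle 7 (SAP 5.1.1).

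**Assumptions, not in the documents.** Time on treatment is exponential with the planned rPFS medians. Each patient's true score is constant, and visit-to-visit noise is the same in both arms.

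**The plan's own figure.** The documents give no expected improver proportion. The nearest stated figure is the 84% rPFS power, which uses the same medians. Power = Φ(√(364 × 2/9) × ln(6/4) − z₀.₉₉₆) = Φ(8.994 × 0.4055 − 2.652) = Φ(0.995) = 84.0%. With the rounded HR of 0.67 it is 82.9%. The planning inputs reproduce.

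**Mechanism.** For k post-baseline scores that are continuous and exchangeable with baseline, P(at least one exceeds baseline) = k/(k+1): 67% at k = 2, 75% at k = 3, 83% at k = 5.

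**Simulation with no true change, 6 against 4 months.** Post-baseline questionnaires average about 5.6 against 4.2.

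| Rule | Longer arm | Shorter arm | Difference (points) |
|---|---|---|---|
| Any rise, continuous score | 78% | 74% | +4 |
| Any rise, discretised utility, noise SD 0.10 | 63% | 59% | +4 |
| 10-point FACT-P rise, noise SD 8 | 44% | 39% | +5 |
| 10-point FACT-P rise, noise SD 10 | 51% | 46% | +5 |

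**Range.** Discretised utility with noise SD 0.05 to 0.15 gives +2.5 to +4.3 points. The FACT-P rule with SD 7 to 14 gives +3.5 to +5.6. The lower ends include the case where a Day 1 Cycle 1 score taken after the randomization baseline also counts, which adds one look in both arms. A cruder model, with an independent chance of 0.1 to 0.4 at each visit, gives about +4 to +8, but it ignores that all visits share one baseline. Other medians: 6 against 5 months, +1 to +4; 8 against 3 or 6 against 2 months, +7 to +22. With equal time on treatment the difference vanishes (58.6% in both arms).

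**Precision.** With 557 × 2/3 ≈ 371 and 557 × 1/3 ≈ 186 patients, a 95% interval for the difference in utility improvers would exclude zero in favour of the longer arm in about 9% to 16% of null trials at 6 against 4 months; 2.5% is expected. The SAP plans per-arm intervals only, so this shows what an informal comparison would do.

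**Worsening.** Counted at any visit, the discretised-utility worsening proportion is also higher in the longer arm, by +1.4 to +3.7 points. For FACT-P the worsening excess equals the improvement excess. One patient can be counted as both.

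**Candidate replacements, same null model.**
- Fixed visit, among patients assessed there: continuous score 50% against 50%; FACT-P with SD 8, P(Z ≥ 10/(8√2)) = 19% in both arms. No artefact.
- Fixed visit, all patients, missing counted as not improved: 0.5 × P(still on treatment), where P = 2^(−days/(median × 30.4375)). Week 12: 0.5 × 0.727 = 36% against 0.5 × 0.620 = 31%. Week 24: 0.5 × 0.529 = 26% against 0.5 × 0.384 = 19%.
- Any-time improvement confirmed at the next questionnaire: 47% against 40%.

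For EQ-5D the last two are further apart than the any-time rule itself.

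**The case against.** The strongest reply is that this figure carries little weight. It is summarized per arm with no between-arm test; quality-of-life p-values are nominal and descriptive, with no alpha control. The between-arm analyses are a stratified Cox model for time to worsening and a repeated-measures model reporting differences at selected time points, and neither uses the any-time count. All of that stands.

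Several stronger readings are tempting, and the documents do not support them:

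- A reader might infer that these proportions mainly measure exposure to testing. The modelled artefact is a few points, and the documents give no expected true benefit to set against it. A decline over time shared by both arms would shrink it.
- A reader might apply k/(k+1) directly to EQ-5D. Utility is discrete with a ceiling at 1: ties are not improvements, and a man already at 1 cannot improve. The discretised model gives about 63% against 59%, not 78% against 74%.
- A reader might see an error that only flatters the investigational arm. Worsening, if counted at any visit, is inflated there too, and the death-score quirk would favour whichever arm has more early deaths.
- A reader might carry over the high early control dropout. The quality-of-life set is the PFS-FAS, randomized after the remedial measures took effect, and no rate is given.

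The death-score point is also limited. The SAP does not say that this score enters the improvement proportion, and a negative baseline utility should be uncommon in men with ECOG 0 to 2 and life expectancy over 6 months (Protocol 4.1). Still, nothing in the text excludes it.

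**Conclusion.** The concern holds, at modest size. The direction follows from the definition whenever one arm is treated longer and scores vary between visits. If time on treatment follows the planned rPFS medians, the excess of improvers with no true change is about 3 to 6 points; it would be smaller if the arms stay on treatment for similar times and larger if control patients leave much sooner. Noise and time on treatment are assumptions, and Protocol 3.4.5 and 5.5 list reasons for stopping other than radiographic progression. The effect is confined to the descriptive improvement proportions for EQ-5D utility and the FACT-P scales, and to the matching worsening proportions if they are counted the same way. BPI-SF has no such improvement proportion. The trial's primary and key secondary conclusions are untouched.

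**What to change.** In SAP 8.2.3.3.1 and 8.2.3.3.2, replace the any-time rule with improvement and worsening status at fixed visits since randomization, for example weeks 12 and 24, with a stated window around each. Report the proportions among patients assessed at that visit, alongside the numbers assessed, dead, off treatment and missing in each arm.

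If a version over all patients with a baseline is also shown, counting missing as not improved, label it as a composite of still being assessed and improved, because it still depends on time on treatment. Confirmation at the next questionnaire does not by itself cure the problem.

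State that the score assigned at death never counts as improvement.

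The cost is SAP wording and simple reprogramming; no new data are needed. The stated improvement rates will be lower. The assessed-only figure is conditional on remaining on treatment, so it describes those patients and not everyone randomized.

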8.2.3.3.2 FACT-P

The Functional Assessment of Cancer Therapy – Prostate (FACT-P) is shown in protocol Appendix 10. The higher the FACT-P score (for all subscales and total scales), the better the QoL.

Description

Scale/Sub-scale Name	Number of Items	Scale Range	FACT-P Item numbers	Threshold for worsening*
Subscale				
Physical Well-Being (PWB)	7 items	0-28	GP1-GP7	3
Social/Family Well-Being (SFWB)	7 items	0-28	GS1-GS7	3
Emotional Well-Being (EWB)	6 items	0-24	GE1-GE6	3
Functional Well-Being (FWB)	7 items	0-28	GF1-GF7	3
Prostate Cancer Subscale (PCS)	12 items	0-48	All items in "Additional Concerns" section	3
PCS pain-related subscale (PRS)	4 items	0-16	P1, P2, P3, GP4	2
FACT Advanced Prostate Symptom Index-8 (FAPSI-8)**	8 items	0-32	GP1, GP4, GE6, C2, P2, P3, P7, P8	3
Total Scale				
Trial Outcomes Index (TOI) score	3 subscales	0-104	PWB, FWB, PCS	9
FACT-G (General)	4 subscales	0-108	PWB, SFWB, EWB, FWB	9
FACT-P Total	39 items	0-156	All	10

*Minimally important difference for both 1) decrease from baseline for within subject change and 2) between group differences for treatment comparisons.

** Symptom index of important clinician-rated symptoms/concerns to monitor when assessing value of treatment for advanced prostate cancer (FAPSI-8; Yount et al. 2003)

Scoring

Scoring of FACT-P subscales and total scores (Trial Outcome Index (TOI), FACT-G Total Score (G for general), and FACT-P Total Score (P for prostate)) are shown below. These are from the FACT-P Scoring Guidelines (Version 4). Item codes in scoring guidelines are shown on the FACT-P form in Appendix 10 of the protocol.

FACT-P Instructions:

- 1) Record answers in "item response" column. If missing, mark with an X
- 2) Perform reversals as indicated, and sum individual items to obtain a score.
- 3) Multiply the sum of the item scores by the number of items in the subscale, then divide by the number of items answered. This produces the subscale score.
- 4) Add subscale scores to derive total scores (TOI, FACT-G, FACT-P).
- 5) Handling missing items. The FACT scale is considered to be an acceptable indicator of patient quality of life as long as **overall item response rate** is greater than 80% (e.g., at least 32 of 39 FACT-P items completed). In addition, a total score should only be calculated if ALL of the component subscales have valid scores. For subscales, as long as **more than** 50% of the items were answered (e.g., a minimum of 4 of 7 items, 4 of 6 items, etc), prorate the subscale score by following the scoring instructions below, producing an observed sum weighted by the inverse of the proportion of observed items.

Subscale	Item Code	Reverse item?	Item response	Item Score	
Physical Well-Being (PWB)	GP1	4 -	=		
	GP2	4 -	=		
	GP3	4 -	=		
	Score range:	GP4	4 -	=	
	0-28	GP5	4 -	=	
		GP6	4 -	=	
		GP7	4 -	=	
Sum individual item scores:					
Multiply by 7:					
Divide by number of items answered:				= PWB subscale score	
Social/Family Well-Being (SFWB)	GS1	0 +	=		
	GS2	0 +	=		
	GS3	0 +	=		
	GS4	0 +	=		
	Score range:	GS5	0 +	=	
	0-28	GS6	0 +	=	
		GS7	0 +	=	
Sum individual item scores:					
Multiply by 7:					
Divide by number of items answered:				= SFWB subscale score	
Emotional Well-Being (EWB)	GE1	4 -	=		
	GE2	0 +	=		
	GE3	4 -	=		
	Score range:	GE4	4 -	=	
	0-24	GE5	4 -	=	
		GE6	4 -	=	
Sum individual item scores:					
Multiply by 6:					
Divide by number of items answered:				= EWB subscale score	
Functional Well-Being (FWB)	GF1	0 +	=		
	GF2	0 +	=		
	GF3	0 +	=		
	Score range:	GF4	0 +	=	
	0-28	GF5	0 +	=	
		GF6	0 +	=	
		GF7	0 +	=	
Sum individual item scores:					
Multiply by 7:					
Divide by number of items answered:				= FWB subscale score	

Subscale	Item Code	Reverse item?	Item response	Item Score
Prostate Cancer Subscale (PCS)	C2	4	-	=
	C6	0	+	=
	P1	4	-	=
	P2	4	-	=
	P3	4	-	=
	P4	0	+	=
	P5	0	+	=
	P6	4	-	=
	P7	4	-	=
	BL2	4	-	=
P8	4	-	=	
BL5	0	+	=	
Sum individual item scores:				
Multiply by 12:				
Divide by number of items answered:				= PC Subscale score

To derive a FACT-P Trial Outcome Index (TOI):

Score range: 0-104

$$\frac{\text{PWB score}}{\text{PWB score}} + \frac{\text{FWB score}}{\text{FWB score}} + \frac{\text{PCS score}}{\text{PCS score}} = \text{FACT-P TOI}$$

To derive a FACT-G Total score:

Score range: 0-108

$$\frac{\text{PWB score}}{\text{PWB score}} + \frac{\text{SFWB score}}{\text{SFWB score}} + \frac{\text{EWB score}}{\text{EWB score}} + \frac{\text{FWB score}}{\text{FWB score}} = \text{FACT-G Total score}$$

To derive a FACT-P Total score:

Score range: 0-156

$$\frac{\text{PWB score}}{\text{PWB score}} + \frac{\text{SFWB score}}{\text{SFWB score}} + \frac{\text{EWB score}}{\text{EWB score}} + \frac{\text{FWB score}}{\text{FWB score}} + \frac{\text{PCS score}}{\text{PCS score}} = \text{FACT-P Total score}$$

To derive Pain-related subscale (PRS):

Subscale	Item Code	Reverse item?	Item response	Item Score
Pain-related subscale	P1	4	-	=
	P2	4	-	=
	P3	4	-	=
Score range: 0-16	GP4	4	-	=
Sum individual item scores:				
Multiply by 4:				
Divide by number of items answered:				= PR Subscale score

To derive FACT Advanced Prostate Symptom Index-8 (FAPSI-8):

Using the 8 items GP1, GP4, GE6, C2, P2, P3, P7, P8, do the following:

Reverse code individual items as needed following guidelines in scores above.

Sum individual item scores.

Multiply by 8.

Divide by the number of items answered.

Analysis

For each FACT-P related total scale and subscale described in the table in the Description section above, will be summarized as continuous variables and will be presented for each time point. A plot of the mean values with standard errors by treatment group at each time point (showing number of subjects at each visit), will be constructed for FACT-P total scale only.

Subscale analysis criteria:

When a treatment difference in the time to worsening in FACT-P total score results in a $p < 0.05$, the FACT-P total subscales defined above (PWB, SFWB, EWB, FWB, PCS) will be analyzed to determine which are associated with the differences.

The proportion of patients that experience improvement relative to baseline in FACT-P total score indicated by a ≥ 10 point increase at any time up through EOT will be summarized as described in Section 8.2.3.3.1 for EQ-5D-5L utility score, and subsequently for the subscales when the .05 criteria described above is met.

The proportion of patients that experience worsening relative to baseline in FACT-P total score indicated by a ≥ 10 point decrease will be summarized similarly.

8.2.3.3.3 BPI-SF

The Brief Pain Inventory - Short Form (BPI-SF) is shown in protocol Appendix 8. The higher the BPI-SF score, the worse the pain.

Description and Scoring

The BPI-SF consists of 4 questions regarding pain intensity, 2 questions on the use of analgesics, and 7 questions on how the level pain has interfered with the subject's life. Intensity items consist of an 11-response rating scale scored from 0 ("No Pain") to 10 ("Pain As Bad As You Can Imagine"). Interference items consist of scores from 0 ("Does Not Interfere") to 10 ("Completely Interferes").

Scale Name	Number of Items	Scale Range	BPI-SF Item numbers	Threshold for worsening*
Individual Item Scales				
Worst pain intensity	1	0-10	3	Either of ≥30% of baseline or ≥2-point increase**
Least pain intensity	1	0-10	4	
Average pain intensity	1	0-10	5	
Pain intensity right now	1	0-10	6	
Summary Scales				
Pain Intensity Scale	4	0-10	3-6	≥30% of baseline
Pain Interference Scale	7	0-10	9a-9g	≥30% of baseline

*Minimally important difference for both 1) increase from baseline for within subject change and 2) between group differences for treatment comparisons.

**Analysis of worst pain intensity is included in Section 8.2.3.4 Health Economics Analysis as time to disease related pain (TDRP).

BPI-SF Intensity is the mean of non-missing items of the 4 items in the table above, if there are 3 or more items not missing; otherwise this scale is set to missing.

BPI-SF Interference scale is the mean of non-missing items of the 7 items in the table above, if there are 4 or more items not missing; otherwise this scale is set to missing.

Analysis

The Pain Intensity Scale, Pain Interference Scale, and the four individual pain intensity items in the table above, will be summarized as continuous variables and will be presented for each time point. A plot of the mean values with standard errors by treatment group at each time point (showing number of subjects at each visit), will be constructed for Pain Intensity Scale, Pain Interference Scale and Worst Pain Intensity Scale, only.

Time to worsening of Worst Pain Intensity (item 3), also called Time to Disease Related Pain (TDRP), Pain Intensity Scale, and Pain Interference Scale are defined as the time (in months) from randomization to the first occurring of 1) an increase of worsening threshold (in the table above) compared to baseline, 2) clinical disease progression (excluding radiographic and PSA progression), or 3) death. If no event is experienced, the censoring date will be time of the last BPI-SF assessment.

Survival analyses of time to worsening of Worst Pain Intensity, Pain Intensity Scale, and Pain Interference Scale will be conducted as described in Section 8.2.3.3.1 for EQ-5D-5L utility score.

Additionally, the time to improvement following initial pain worsening in Pain Intensity Scale and Pain Interference Scale will be analyzed using mixture distribution methodology described in Section 8.2.2. Time to pain improvement is defined as time from worsening of intensity or interference to a score \leq baseline.

Change from baseline in Worst Pain Intensity, Pain Intensity Scale, and Pain Interference Scale will also be analyzed using general linear models for repeated measures as described in Section 8.2.3.3.1 for EQ-5D-5L utility score.

